#### Time between VIBLOK application and sampling

The relation between the timing of the post VIBLOK sample and the difference between the pre and post VIBLOK HSV-2 sample values will be explored by a graph (x-axis will be the timing, y-axis will be the difference in HSV-2 values).

#### Shaving and waxing habits

- The genital grooming habits in relation to the pre-VIBLOK HSV-2 sample value will be explored by descriptive statistics of the pre-VIBLOK HSV-2 sample value by grooming habit (None / Shaving / Waxing / Other) and by frequency of habit (Daily / Weekly / Monthly / Other / No Shaving habit).

- The genital grooming habits in relation to the difference between the pre and post VIBLOK HSV-2 sample value will be explored by descriptive statistics of the difference between the pre and post VIBLOK HSV-2 sample value by grooming habit (None / Shaving / Waxing / Other) and by frequency of habit (Daily / Weekly / Monthly / Other / No Shaving habit).
- Participant satisfaction using VIBLOK as assessed on the participant questionnaire Frequency distributions will be presented for
  - Ease of use of VIBLOK (Very easy to use / Somewhat easy to use / Difficult to use)
  - The use of VIBLOK (Simple and clear / Somewhat confusing / Very confusing)
  - VIBLOK user documentation (Excellent / Adequate / Inadequate)
  - Use of VIBLOK if VIBLOK was available for use (Participant would use it / Participant would use it only in very special cases / Participant would never use it)Only listings will be provided for
  - The best participant liked about VIBLOK
  - The least participant liked about VIBLOK
  - Suggestions of participant for improving VIBLOK
- Symptoms (Itching, burning, tingling / Lesions (sores, blisters, ulcers, crusts) / Other) as recorded on the participant's diary.
  - Any symptoms (Yes / No)
  - The percentage of days with any symptoms in relation to total number of days of participation.
  - Any Itching, burning, tingling (Yes / No)
  - The percentage of days with any Itching, burning, tingling in relation to total number of days of participation.
  - Any lesions (sores, blisters, ulcers, crusts) (Yes / No)
  - The percentage of days with any lesions in relation to total number of days of participation.
  - Any other symptom (Yes / No)
  - The percentage of days with any other symptom in relation to total number of days of participation.
- Location of the lesion (Genitals / Rectal (perineum, perianal) / Buttock / Other) as recorded on the participant's diary.
  - Any location (Yes / No)
  - The percentage of days with any location in relation to total number of days of participation.
  - Any rectal (perineum, perianal) location (Yes / No)
  - The percentage of days with any rectal location in relation to total number of days of participation.
  - Any buttock location (Yes / No)
  - The percentage of days with any buttock location in relation to total number of days of participation.
  - Any other location (Yes / No)

- The percentage of days with any other location in relation to total number of days of participation.

All exploratory analyses will be based on the As Treated Population. These analyses will not be repeated for the Per Protocol Population.

## 5. Safety Evaluation

### 5.1 Extent of Exposure

The duration of exposure will be assessed as the number of days between the date of Visit 1 (Day 1) and the date of the last date of diary completion with non-missing time skin or VIBLOK swab collected.

The duration of exposure will be summarized for the As Treated Population and Per Protocol Population.

### 5.2 Adverse Events

#### 5.2.1 Primary endpoint

The primary endpoint of this study is a safety endpoint:

The number of Serious Adverse Device Effects during minimally 26 days of VIBLOK use. A two-sided exact 95% Clopper-Pearson confidence interval will be calculated. The study will be considered a success in case the upper limit of the 95% confidence interval is below 10%.

The analysis will be based on the As Treated Population and repeated for the Per Protocol Population.

#### 5.2.2 Display of adverse events

All adverse events occurring after initiation of study treatment (including events likely to be related to the underlying disease or likely to represent concomitant illness) will be displayed in summary tables.

The tables will list each adverse event, the number of participants in whom the event occurred, and the rate of occurrence.

Adverse events will be grouped by the following categories:

- Any event
- Bleeding / Anaemia
- Bowel
- Cardiac
- Malignancies
- Miscellaneous
- Neurological
- Pulmonary
- Renal
- Urogenital
- Vascular
- Genital

- Skin
- Infection
- Trauma
- Other

The analysis of adverse events comprises the following categories:

- Any adverse event
- Any adverse event by consideration
- Adverse events considered to be a toxic reaction
- Adverse events considered to be an allergic reaction
- Adverse events considered to be an infection
- Adverse events considered to be other
- Any adverse event by severity
- Possibly, probably or definitely related to investigational device adverse events
- Possibly, probably or definitely related during application of the investigational device adverse events
- Possibly, probably or definitely related after application of the investigational device adverse events
- Possibly, probably or definitely related to study procedure adverse events
- Adverse events related to a pre-existing / other medical condition
- Adverse event related complications associated with an HSV 2 infection
- Any adverse event
- Recurrence of genital herpes
- Systemic symptoms
- Fever
- Headache
- Malaise
- Myalgia(s)
- Local pain and itching
- Dysuria
- Tender lymphadenopathy
- Unanticipated adverse events
- Adverse events by action taken
- No action taken
- Drug Therapy
- Any
- Prescription
- Non-Prescription
- Surgical intervention or other invasive therapy
- Hospitalization
- Other treatment / procedure
- Withdraw from study due to AE
- Adverse events by outcome
- Resolved
- Resolved with sequelae
- Ongoing
- Ongoing at time of exit
- Unknown / Lost to Follow-up

- Death
- Reportable adverse events

Serious adverse events will only be listed as it will be expected that there will only be very few or no serious adverse event.

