7.1. Definitions

An Adverse Event (AE) is any untoward medical occurrence, unintended disease or injury, or untoward clinical signs (including abnormal laboratory findings) in subjects, users or other persons, whether or not related to the investigational medical device.

A Serious Adverse Event (SAE) is any adverse event that:

- a) leads to death
- b) leads to a serious deterioration in the health of the subject that
 1. results in a life-threatening illness or injury
 2. results in a permanent impairment of a body structure or a body function
 3. requires in-patient hospitalization or prolongation of existing hospitalization
 4. results in medical or surgical intervention to prevent permanent impairment to a body structure or a body function
- c) leads to fetal distress, fetal death, congenital abnormality or birth defect

Adverse Device Effects and Serious Adverse Device Effects are those AEs and SAEs that occur as an untoward or unintended response to a medical device. These events include those which result from insufficiencies or inadequacies in the Instructions for Use or deployment of the device as well as user error.

Unanticipated Serious Adverse Device Effect (USADE) is defined as any serious adverse effect on health or safety or any life-threatening problem or death caused by – or associated with – the device, if that effect, problem or death was not previously identified in nature, severity, or degree of incidence in the investigational plan (including documents such as the protocol, Investigator's Brochure, informed consent form or other study-related documents), or any other unanticipated serious problem associated with the device that relates to the rights, safety or welfare of subjects.

Adverse events may be volunteered by participants, elicited from questioning by Investigator or designee, or collected via observation by the Investigator. In addition, participants will be instructed to contact the investigator, and/or study coordinator if any significant adverse events occur between study evaluation visits.

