8.5. Definitions

The definitions used in this protocol are consistent with those referenced in ISO 14155:2011.

Term	Definition	Reference/Justification
Adverse Event (AE)	Any untoward medical occurrence, unintended disease or injury, or untoward clinical signs (including abnormal laboratory findings) in subjects, users or other persons, whether or not related to the investigational device.	ISO 14155: 2011

Term	Definition	Reference/ Justification
Serious Adverse Event (SAE)	
Adverse Event that:
 
 a) led to a death, b) led to a serious deterioration in the health of a study subject that 
 • resulted in a life-threatening illness or injury, • resulted in permanent impairment of a body structure or body function, • required in-patient hospitalization or prolongation of existing hospitalization, • resulted in a medical or surgical intervention to prevent permanent impairment to body structure or a body function. c) leads to fetal distress, fetal death or a congenital abnormality or birth defect 
The following is not considered an SAE: Hospitalization for diagnostic or elective surgical procedures, planned at or before the enrollment for a pre-existing condition.
	ISO 14155: 2011
Adverse Device Effect (ADE)	
Adverse event related to the use of an investigational medical device.
 
This definition also includes adverse events resulting from insufficient or inadequate instructions for use, deployment, implantation, installation, or operation, or any malfunction of the investigational device. And events resulting from use error or from intentional misuse.
	ISO 14155: 2011
Serious Adverse Device Effect (SADE)	Adverse Device Effect that resulted in any of the consequences characteristics of a Serious Adverse Event.	ISO 14155: 2011
Unanticipated Adverse Device Effect (UADE)	Any serious adverse effect on health or safety or any life-threatening problem or death caused by, or associated with, a device, if that effect, problem, or death was not previously identified in nature, severity, or degree of incidence in the investigational plan or application (including a supplementary plan or application), or any other unanticipated serious problems associated with a device that relates to the rights, safety, or welfare of patients.	ISO 14155: 2011

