Device Malfunction or deterioration	Failure of a device to perform in accordance with its intended purpose when used in accordance with the manufacturer's instructions.	GHTF/SG2/N 54R8:2006
Endpoints, Clinical Safety (after 26 days)	
 • SADE incidence • Nature, frequency, duration, severity, seriousness and causality of adverse events 	
Endpoints, Performance (after 26 Days)	
 • Comparison of HSV detection rate on days with asymptomatic shedding prior and after applying VIBLOK • Comparison of HSV copy number on days with asymptomatic shedding prior and after applying VIBLOK 	
Pre-Existing Condition	A pre-existing condition is one that is present at the start of study treatment. A preexisting condition is not an adverse event unless it worsens as a result of the study treatment.	
Recurrent Hospitalization Re-Hospitalization	Re-hospitalization for HSV-2 recurrences and/or complications related to the cream.	

9. Statistical Considerations

This clinical study is a prospective, non-randomized, comparative multi-center safety and performance trial.

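### SAP 5.2.2 tabulates all adverse events but then says serious ones will only be listed; on either reading no table gives the number and percentage of participants with a serious adverse event

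*SAP*

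**What the plan says.** SAP 5.2.2 sets the scope of the summary tables broadly: "All adverse events occurring after initiation of study treatment", with events of the underlying disease and concomitant illness expressly included. On content it says: "The tables will list each adverse event, the number of participants in whom the event occurred, and the rate of occurrence". The planned breakdowns include any event, severity, relation to device and procedure, action taken (with a row for hospitalization) and outcome (with a row for death). None is by seriousness. The section closes with: "Serious adverse events will only be listed as it will be expected that there will only be very few or no serious adverse event".

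Other SAP sections also deal with serious events:
- 5.2.1 analyses serious adverse device effects (SADEs), the primary endpoint, with an exact two-sided 95% interval.
- 5.2.3 lists every adverse event by participant, with seriousness as a field.
- 5.3.1 lists deaths and other SAEs.
- 5.3.2 gives narratives, except for events clearly unrelated to the cream.
- 2.8 prescribes exact Clopper-Pearson intervals for categorical variables.

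Protocol 8.5 describes the clinical safety endpoint as SADE incidence together with "Nature, frequency, duration, severity, seriousness and causality of adverse events", and the synopsis lists the same attributes. Protocol 9.5.2 and SAP 1.3 shorten this to the total number and type of events, and SAP 1.3 makes the analysis descriptive only.

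**The concern.** Every SAE is an adverse event, so a rule that all adverse events are tabulated and a rule that serious ones are only listed cannot both be followed to the letter. The reason given, that few or none are expected, is a reason for not tabulating them, so a programmer could take the closing sentence as an instruction to leave them out. The any-event, severity and device-related rates would then omit the gravest events.

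The second problem does not depend on that reading. Safety is the primary objective and the data are meant to support CE marking, yet no table states the proportion of participants with an SAE of any cause. In a single-arm, open-label trial that figure has particular value because it does not depend on anyone's judgement of causality. The SADE count does.

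**Working it through.** **1. The plan's own figure.** The SAP states no number for the display of SAEs. Its only serious-event figure is the sample size for the SADE endpoint: 36 participants for an upper limit below 10% (SAP 1.4). With no events, the two-sided exact 95% upper limit is 1 − 0.025^(1/n).
- n = 35: 10.003%, just above 10%
- n = 36: 9.74%

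So 36 reproduces, and it does not depend on how SAEs are displayed.

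**2. The two readings side by side.** Protocol 7.1 makes an adverse event serious if it leads to death or "requires in-patient hospitalization or prolongation of existing hospitalization". Protocol 8.5 exempts "Hospitalization for diagnostic or elective surgical procedures, planned at or before the enrollment for a pre-existing condition".

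| Planned output in SAP 5.2.2 | SAEs excluded from tables (literal) | SAEs kept in tables, no separate SAE table |
|---|---|---|
| Any event, severity, device-related rows | Non-serious events only | All events |
| Death row | Empty by definition | Counts deaths |
| Hospitalization row | Exempt planned stays only | Counts all hospitalizations |
| Participants with an SAE, n and % | Not tabulated | Not tabulated |

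The first three lines depend on the reading. The last does not.

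**3. What the missing row would show.** Assume 46 treated participants, the planned number applying the cream, all contributing safety data. The event counts are illustrative. For x participants with an SAE out of n, the exact 95% limits are:
- lower = Beta quantile at 0.025 with parameters (x, n − x + 1), or 0 if x = 0
- upper = Beta quantile at 0.975 with parameters (x + 1, n − x)

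| Participants with an SAE | Rate | Exact 95% interval |
|---|---|---|
| 0/46 | 0% | 0 to 7.7% |
| 1/46 | 2.2% | 0.06% to 11.5% |
| 2/46 | 4.3% | 0.5% to 14.8% |

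**4. What SAP 5.2.1 covers.** If no SAE occurs there is no SADE either, and 5.2.1 already yields 0/46 with an upper limit of 7.7%. The two diverge when an SAE is judged unrelated. With two participants whose SAEs are both judged unrelated, 5.2.1 would still report 0/46 (0 to 7.7%), while the all-cause result is 2/46 (4.3%, 0.5% to 14.8%). Those two events would appear in the listings. If they were judged clearly unrelated, 5.3.2 would give them no narrative.

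**The case against.** The strongest reply is that the SAP never says SAEs are removed from the summary tables. Its scope statement has no exception for them. By the protocol's definition every death is serious, so a plan that barred SAEs from the tables would have no reason to include a death row. The closing sentence more naturally means that SAEs get no separate summary because few are expected. This stands. A reader might infer that the tables leave out the worst events, that the hospitalization and death rows will read zero, or that the adverse event rates are biased downwards. The documents do not establish any of these. They are consequences of a literal reading that the text permits but the planned rows argue against.

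A reader might also infer that the SAE frequency is never produced. That is too strong. With about 46 participants it can be counted from 5.2.3 and 5.3.1, and SADEs have their own analysis. What is absent is a tabulated all-cause rate with its interval. The planned category for reportable adverse events does not supply it, because the SAP does not define that term or equate it with serious.

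Finally, it can be said that the secondary safety endpoint in Protocol 9.5.2 and SAP 1.3 is only the number and type of events. That is correct for those sections. The synopsis and Protocol 8.5 nevertheless name frequency and seriousness, so the objection weakens the endpoint argument but does not remove it.

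**Conclusion.** The point holds, and it is minor. SAP 5.2.2 contains two statements that cannot both be followed literally. On either reading it plans no count and percentage of participants with an SAE. The primary analysis, the success criterion and the sample size are unaffected.

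The consequence is one of clarity and completeness in the safety report. At 46 treated, the rate left untabulated would carry an upper limit of 7.7% if no SAE occurs, and an interval of 0.5% to 14.8% if two participants have one. Those figures assume that all 46 contribute safety data, and the event counts are examples, not forecasts. An expectation of few events is a reason to give the interval, since an empty listing does not show what rate the trial can exclude.

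**What to change.** Replace the closing sentence of SAP 5.2.2 with: *Serious adverse events are included in all adverse event summary tables and are additionally listed individually (5.3.1).*

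Add one row to the tables: participants with at least one SAE, giving n, %, number of events and the exact 95% Clopper-Pearson interval for the proportion of participants. A separate SADE row is not needed because 5.2.1 covers it.

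The cost is one SAP sentence and one table row. Seriousness is already recorded for every event in the 5.2.3 listing, and SAP 2.8 already prescribes the interval method, so no new data and no new method are required.

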### **5.2.3 Listings of adverse events by participant**

All adverse events for each participant, including the same event on several occasions will be listed, giving both the adverse event classification and the original description used by the investigator. The listing will be by investigator and will include:

- Participant identifier
- Age, race, sex, weight
- The adverse event (adverse event classification, reported term) • Diagnostic test and test results
- Duration of the adverse event
- Seriousness
- Severity (e.g. mild, moderate, severe, life threatening)
- Causality assessment (relatedness).
- Action taken
- Outcome
- Date of onset
- Date PI or site became aware of (S)AE

Any abbreviations and codes will be clearly explained on each page.

## **5.3 Deaths, other serious adverse events, and other significant adverse events**

### **5.3.1 Listing of deaths, other serious adverse events, and other significant adverse events**

Listings, containing the same information as called for in section 5.2.3 above, will be provided for the following events.

#### **5.3.1.1 Deaths**

All deaths during the study will be listed by participant.

#### **5.3.1.2 Other serious adverse events**

All serious adverse events (other than death but including the serious adverse events temporally associated with or preceding the deaths) will be listed.

[figure not shown]
#### **5.3.1.3 Other significant adverse events**

Any events that led to an intervention, including withdrawal of VIBLOK or significant additional concomitant therapy, other than those reported as serious adverse events, will be listed.

**5.3.2 Narratives of deaths, other serious adverse events, and certain other significant adverse events**

There will be brief narratives describing each death, each other serious adverse event, and those of the other significant adverse events that are judged to be of special interest because of clinical importance. Events that were clearly unrelated to VIBLOK will be omitted.

**6. ANNEX I DISPOSITION OF PARTCIPANTS**

## 7. ANNEX II LISTING OF PARTICIPANTS WHO DISCONTINUED STUDY PRODUCT

Centre: X1

Participant: yyy

| Reason for Discontinuation | Age | Last Visit | Duration | Concomitant Medication |
|----------------------------|-----|------------|----------|------------------------|
|----------------------------|-----|------------|----------|------------------------|

|                  |    |   |    |              |
|------------------|----|---|----|--------------|
| Lost to followup | 67 | 2 | 15 | Medication y |
|------------------|----|---|----|--------------|

Centre: X1

Patient: zzz

| Reason for Discontinuation | Age | Last Visit | Duration | Concomitant Medication |
|----------------------------|-----|------------|----------|------------------------|
| Lack of efficacy           | 45  | 2          | 12       | Medication z           |

Centre: X2

Patient: xxx

| Reason for Discontinuation     | Age | Last Visit | Duration | Concomitant Medication |
|--------------------------------|-----|------------|----------|------------------------|
| Withdrawal of informed consent | 22  | 1          | 20       | Medication x           |

#### 8. ANNEX III LISTING OF PARTICIPANTS AND OBSERVATIONS EXCLUDED FROM ANALYSES

Centre: X1

Patient: yyy

| Age | Parameter | Visit | Analysis Set            | Reason (s)                            |
|-----|-----------|-------|-------------------------|---------------------------------------|
| 67  | all       | all   | Per Protocol Population | Did not complete 26 days of treatment |
